12.5.1.3. Events NOT Meeting the AE Definition

- Situations where an untoward medical occurrence did not occur (e.g. social and/or convenience admission to a hospital, admission for routine examination).
- Anticipated day-to-day fluctuations of pre-existing disease(s) or condition(s) present or detected at the start of the study that do not worsen.
- Pre-existing conditions or signs and/or symptoms present in a subject prior to the first study vaccination. These events will be recorded in the medical history section of the eCRF.
- Medical or surgical procedures (e.g. endoscopy, appendectomy); the condition that leads to the procedure is an AE/SAE.

12.5.2. Definition of SAE

An SAE is any untoward medical occurrence that:

- a. Results in death,
- b. Is life-threatening,

Note: The term 'life-threatening' in the definition of 'serious' refers to an event in which the subject was at risk of death at the time of the event. It does not refer to an event, which hypothetically might have caused death, had it been more severe.

- c. Requires hospitalization or prolongation of existing hospitalization,

Note: In general, hospitalization signifies that the subject has been admitted at the hospital or emergency ward for observation and/or treatment that would not have been appropriate in the physician's office or in an out-patient setting. Complications that occur during hospitalization are also considered AEs. If a complication prolongs hospitalization or fulfils any other serious criteria, the event will also be considered serious. When in doubt as to whether 'hospitalization' occurred, or was necessary, the AE should be considered serious.

Hospitalization for elective treatment of a pre-existing condition (known or diagnosed prior to informed consent signature) that did not worsen from baseline is NOT considered an AE.

- d. Results in disability/incapacity, OR

Note: The term disability means a substantial disruption of a person's ability to conduct normal life functions. This definition is not intended to include experiences of relatively minor medical significance such as uncomplicated headache, nausea, vomiting, diarrhoea, influenza like illness, and accidental trauma (e.g. sprained ankle) which may interfere or prevent everyday life functions but do not constitute a substantial disruption.

- e. Is a congenital anomaly/birth defect in the offspring of a study subject.

Medical or scientific judgement should be exercised in deciding whether reporting is appropriate in other situations, such as important medical events that may not be immediately life-threatening or result in death or hospitalization but may jeopardize the subject or may require medical or surgical intervention to prevent one of the other outcomes listed in the above definition. These should also be considered serious.

Examples of such events are invasive or malignant cancers, intensive treatment in an emergency room or at home for allergic bronchospasm, blood dyscrasias or convulsions that do not result in hospitalization.

All AEs which do not fall into these categories are defined as non-serious.

It should be noted that a severe AE need not be serious in nature and that a SAE need not, by definition, be severe.

SAEs will be captured both on the Vaccines Serious Adverse Event (VSAE) form as well as on the AE eCRF. All SAEs will be evaluated by the investigator for relationship of the event to study vaccine.

12.5.3. Solicited adverse events

The term “reactogenicity” refers to solicited signs and symptoms (“solicited adverse events”) occurring in the hours and days following a vaccination, to be collected by the subjects/parent(s)/LAR(s) for 7 consecutive days (with ongoing solicited AEs collected until resolution or day 30, whichever occurs first), using a pre-defined Subject Diary .

The following solicited adverse events are included in the Subject Diary. Each adverse event is to be assessed using the scoring system reported in parentheses below:

The collected data will be entered into the Subject eDiary. Please see Section 12.5.8 for more detail.

a. Solicited local (injection-site) adverse events

The following local (injection-site) AEs will be solicited:

Table 26 Solicited local adverse events*

All age groups
Pain at injection site
Redness at injection site
Swelling at injection site
Induration at injection site

* Solicited local AEs occurring within 30 minutes after vaccination.

b. Solicited systemic adverse events

The following systemic AEs will be solicited:

Table 27 Solicited systemic adverse events

Adolescents (from 11 years of age) and adults
Fatigue
Fever (body temperature $\geq 38.0^{\circ}\text{C}/100.4^{\circ}\text{F}$)
Nausea
Headache
Myalgia
Arthralgia

Note: Subjects/parent(s)/LAR(s) will be instructed to measure and record the body temperature (preferably oral) in the evening. Should additional temperature measurements be performed at other times of day, subjects/parent(s)/LAR(s) will be instructed to record the highest temperature in the eDiary.

The study staff must review the data entered into the Subject Diary as described in Section [12.5.8](#).

12.5.3.1. Other Solicited Adverse Events

The use of analgesics/antipyretics for either prophylactic or treatment purposes will be recorded as other solicited events in the Subject Diary (eDiary) and subsequently recorded onto the eCRFs and subject medical records.

The study staff must review the data entered into the Subject Diary as described in Section [12.5.8](#).

Note: Any solicited adverse event that meets any of the following criteria must be entered into subjects' source document (see Section [12.5.8](#)) and also as an adverse event on the Adverse Event eCRF:

- Solicited local or systemic adverse event that leads to a visit to a healthcare provider (medically attended adverse event, see Section [12.5.8.3.3](#)).
- Solicited local or systemic adverse event leading to the subject withdrawing from the study or the subject being withdrawn from the study by the investigator (adverse event leading to withdrawal).
- Solicited local or systemic adverse event that otherwise meets the definition of a serious adverse event (see Section [12.5.2](#)).

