4. OBJECTIVE(S) AND ENDPOINT(S)

Table 6 Study objectives and endpoints (Amended 11 October 2022)

Objectives	Endpoints
Primary	
To assess the safety and tolerability of rMenB+OMV NZ and MenACWY, when administered concomitantly or alone, in healthy subjects 16-18 years of age.	
 • The frequencies and percentages of subjects with solicited local (i.e., injection site pain, erythema, swelling, induration) and systemic (i.e., fever [temperature $\geq 38.0^{\circ}\text{C}/100.4^{\circ}\text{F}$], nausea, fatigue, myalgia, arthralgia, headache) adverse events (AEs) during the 7 days (including the day of vaccination) following the first (Visit 1, Day 1/Month 0), the second (Visit 3, Month 2) and the third (Visit 4, Month 3) vaccination for all groups. • The frequencies and percentages of subjects with any unsolicited AEs (including all SAEs), AEs leading to withdrawal and medically attended AEs during the 30 days (including the day of vaccination) following the first (Visit 1, Day 1/Month 0), the second (Visit 3, Month 2) and the third (Visit 4, Month 3) vaccination for all groups. • The frequencies and percentages of subjects with SAEs, AEs leading to withdrawal, and medically attended AEs, throughout the study period (Day 1/Month 0 to Month 9). • The frequencies and percentages of subjects (who received rMenB+OMV NZ) with AESI throughout the study period (Day 1/Month 0 to Month 9). • Among subjects who are followed for 12 months after their last dose: 
 ○ The frequencies and percentages of subjects with

CONFIDENTIAL

205419 (MENB REC 2ND GEN-045 (V72_79))

Protocol Amendment 7 Final

Objectives	Endpoints
	
SAEs, AEs leading to withdrawal, between SFU 5 (Month 9) and SFU 7 (Month 15).
 
The frequencies and percentages of subjects (who received rMenB+OMV NZ) with AESI between SFU 5 (Month 9) and SFU 7 (Month 15).

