8.2. Pre-vaccination procedures

8.2.1. Data Collected from Subjects

The following data will be collected from each subject over the duration of their study participation:

- Demographic Information.
- Medical history (any significant past diagnoses including allergies, hospitalizations, surgeries requiring in-patient hospitalization, any other medical conditions which may impair the assessment of safety of the rMenB+OMV NZ and MenACWY vaccines).
- Vaccination history as confirmed by vaccination records, if accessible.
- Pre-vaccination body temperature.
- Post-vaccination immediate reactions observed for at least 30 minutes after injection: signs or symptoms of anaphylaxis, allergic phenomena (such as rashes, itching, or other allergic manifestations). Local and systemic solicited data (including e.g., use of medication to treat or prevent fever, and/or pain).
- Post-vaccination solicited local and systemic AEs collected at home by subject and/or subject's parent(s)/LAR(s) and recorded on Subject Diary (eDiary) for 7 days following each vaccination visit.
- Adverse Events.
 - Unsolicited AEs occurring within 30 days after each vaccination will be collected for all subjects by interviewing the subject and/or subject's parent(s)/LAR(s) (as applicable) during the site visits or Safety Follow-up Calls and by reviewing of available medical records.
 - SAEs occurring during the entire study period

- Medically attended AEs occurring during the entire study period
- AEs leading to premature withdrawal from the vaccination/study occurring during the entire study period
- AESI occurring during the entire study period (for subjects who received rMenB+OMV NZ)
- Prior and concomitant medication as defined in Section [7.5](#).

All data collected must only be identified using the GSK Subject ID, as described in Section [7.2](#), documented in the source documents and entered in the eCRF*.

*Only the solicited local and systemic AEs 30 minutes post vaccination are entered in the eCRF. The solicited local and systemic AEs during 7-day post-vaccination period are not entered in the eCRF and are documented only in eDiary.

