For any subject withdrawn from study participation prior to the planned Study Termination Call, it is important to determine if an AE was associated with the reason for discontinuing the study. This AE must be identified on the AE eCRF page by indicating "Withdrawn from study due to AE". Any ongoing AEs at the time of study withdrawal must be followed until resolution or stabilization.

Subjects who develop a SAE judged to be possibly related to the study vaccine, including hypersensitivity reactions, should not receive subsequent vaccination.

Death:

For any subject withdrawn from study participation due to death, this should be noted on the Study Termination eCRF page and the associated SAE that led to the death must be reported.

Withdrawal of consent:

The subject and/or parent(s)/LAR(s) can withdraw consent for participation in the study at any time without penalty or loss of benefit to which the subject is otherwise entitled. Reason for early termination should be deemed as “withdrawal of consent” if the subject withdraws from participation due to a non-medical reason (i.e., reason other than AE). If the subject and/or parent(s)/LAR(s) intend(s) to withdraw consent from the study, the investigator should clarify if the subject will withdraw completely from the study or if the subject will continue study participation for safety, or a subset of other study procedures. If the subject requests complete withdrawal from the study, no further study interventions will be performed with the subject.

If a subject and/or parent(s)/LAR(s) withdraw(s) consent but does not revoke the HIPAA (The Health Insurance Portability and Accountability Act) authorization, the Sponsor will have full access to the subject’s medical records, including termination visit information. If a subject and/or parent(s)/LAR(s) revokes only the HIPAA authorization, the Sponsor will have full access to all of the subject’s medical records prior to the date and time of written revocation.

Lost to Follow-Up:

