9.2. Discontinuation of study vaccine(s)

A 'withdrawal' from the study vaccine(s) refers to any subject who does not receive the complete treatment, i.e. when no further planned dose is administered from the date of withdrawal. A subject withdrawn from the study vaccine(s) may continue further study procedures (safety or immunogenicity) if planned in the study protocol, as deemed appropriate by the investigator.

Primary reason relative to premature discontinuation of the study vaccine(s) will be documented on the Vaccine Administration page/screen of the eCRF. The investigator will document whether the decision to discontinue further vaccination/treatment was made by the subject himself/herself, by the subject's parent(s)/LAR(s), or by the investigator, as well as which of the following possible reasons was responsible for withdrawal:

- Adverse event requiring expedited reporting
- Non-serious AE (specify)
- Unsolicited non-serious AE
- Solicited adverse event
- Not willing to be vaccinated
- Other (specify).

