The time period for collecting and recording SAEs will begin at the first receipt of study vaccines and will end 12 months following administration of the last dose of study vaccines for each subject. See Section 12.5.9 for instructions on reporting of SAEs. However, any SAEs assessed as related to study participation (e.g. study treatment, protocol-mandated procedures, invasive tests, or change in existing therapy) or related to a GSK Biologicals product will be recorded from the time a subject consent to participate in the study.

All AEs occurring after the ICF is signed but prior to receiving study vaccine will be documented as an AE and recorded within source document and eCRF. However, any AEs occurring prior to receipt of any study vaccine will be analyzed separately from "treatment emergent" AEs (AEs occurring after administration of the first study vaccine). All AEs/SAEs leading to withdrawal from the study will be collected and recorded from the time of the first receipt of study vaccines until study end.

In addition to the above-mentioned reporting requirements and in order to fulfil international reporting obligations, SAEs that are related to study participation (i.e. protocol-mandated procedures, invasive tests, a change from existing therapy) or are related to a concurrent GSK Biologicals medication/vaccine will be collected and recorded from the time the subject consents to participate in the study until she/he is discharged from the study.

The time period for collecting and recording pregnancies will begin at the first receipt of study vaccines and will end 12 months following administration of the last dose of study vaccines. See section [12.5.9](#) for instructions on reporting of pregnancies.

The time period for collecting and recording of AESIs will begin at the first receipt of study vaccines and will end 12 months following administration of the last dose of study vaccines. See section [12.5.9.5](#) for instructions on reporting of AESIs.

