There may be situations when a SAE has occurred and the investigator has minimal information to include in the initial report to GSK Biologicals. However, it is very important that the investigator always makes an assessment of causality for every event prior to submission of the Expedited Adverse Events Report to GSK Biologicals. The investigator may change his/her opinion of causality in light of follow-up information and update the SAE information accordingly. The causality assessment is 1 of the criteria used when determining regulatory reporting requirements.

All solicited local (injection site) reactions will be considered causally related to vaccination. Causality of all other AEs should be assessed by the investigator using the following question:

Is there a reasonable possibility that the AE may have been caused by the study vaccine?

YES	: There is a reasonable possibility that the study vaccines contributed to the AE.
NO	: There is no reasonable possibility that the AE is causally related to the administration of the study vaccine(s). There are other, more likely causes and administration of the study vaccine(s) is not suspected to have contributed to the AE.

If an event meets the criteria to be determined as ‘serious’ (see Section 12.5.2), additional examinations/tests will be performed by the investigator in order to determine ALL possible contributing factors for each SAE.

Possible contributing factors include:

- Medical history.
- Other medication.
- Protocol required procedure.
- Other procedure not required by the protocol.
- Lack of efficacy of the vaccine(s), if applicable.
- Erroneous administration.
- Other cause (specify).

AEs will also be evaluated by the investigator for the co-existence of any of the other following conditions:

“Medically attended AEs”: an AE that leads to a visit to a healthcare provider.

AEs leading to withdrawal: AEs leading to study or vaccine withdrawal.

If solicited or unsolicited AEs have been reported and the subject and/or parent(s)/LAR(s) indicated that the symptoms required medical attendance or were of concern, the subject and/or parent(s)/LAR(s) must be contacted for further information.

When the subject and/or parent(s)/LAR(s) is contacted for any of these reasons, the contact must be documented in the subject’s source documentation.

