5.5.1.3. Analysis of Unsolicited Adverse Events

All safety analyses will be performed using the Exposed set.

This analysis applies to all AEs occurring during the study, judged either as probably related, possibly related, or not related to vaccination by the investigator, recorded in AE eCRF, with a start date on or after the date of first vaccination. All AEs starting prior to the first vaccination will only be listed. The original verbatim terms used by investigators to identify AEs in the eCRFs will be mapped to preferred terms using the MedDRA dictionary. The AEs will then be grouped by MedDRA preferred terms into frequency tables according to system organ class.

All reported AEs, as well as AEs judged by the investigator as at least possibly related to study vaccine, will be summarized according to system organ class and preferred term within system organ class. These summaries will be presented by vaccination group and by interval of study observation. When an AE occurs more than once for a subject, the maximal severity and strongest relationship to the group will be counted.

Separate summaries will be produced for the following categories:

- Serious adverse events (SAEs)
- Adverse Events of Special Interest (AESIs) for subjects who received rMenB+OMV NZ

- Adverse events that are possibly or probably related to vaccine.
- Adverse event leading to withdrawal with relationship to COVID-19.
- Adverse events leading to a medically attended visit.

The frequencies and percentages of subjects who reported at least one immediate unsolicited adverse event (i.e., reactions that occurred during the first 30 minutes after any vaccination that have been flagged as immediate in the eCRF and have not been reported in the eDiary) following any study vaccination will be reported by study group.

Data listings of all AEs will be provided by subject. In addition, AEs in the categories above will be provided as listed data.

Between groups assessment

No statistical tests for between-group comparisons will be performed.

- The percentages of subjects with any unsolicited AEs (including all SAEs) during the 30 days (including the day of vaccination) following the first (Visit 1), the second (Visit 3) and the third (Visit 4) vaccination for all groups will be calculated.

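### AEs leading to withdrawal, a primary safety endpoint, covers study or vaccine withdrawal in some protocol sections and study withdrawal only in others, so a solicited reaction that stops vaccination may go uncounted

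*Protocol*

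**What the plan says.** Protocol Section 4 (Table 6) lists among the primary safety endpoints "The frequencies and percentages of subjects with SAEs, AEs leading to withdrawal, and medically attended AEs, throughout the study period", from Day 1 to Month 9. The same category is also an endpoint for the 30 days after each vaccination. Neither place says whether the withdrawal is from the vaccine or from the study, and SAP Section 2 repeats the wording.

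Elsewhere the protocol gives the term two meanings:

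- **Vaccine or study.** Section 8.2.1 lists "AEs leading to premature withdrawal from the vaccination/study occurring during the entire study period". Section 12.5.8.3.2 gives "AEs leading to withdrawal: AEs leading to study or vaccine withdrawal". The Schedule of Activities (Table 3) and Section 12.5.4 also cover vaccine withdrawal, but only for unsolicited AEs.
- **Study only.** Section 12.5.8.2 says "All AEs/SAEs leading to withdrawal from the study will be collected and recorded". The matching row of Tables 15 and 16 is also limited to the study. Section 12.5.3.1 sets out when a solicited AE must also be entered on the AE eCRF. One criterion is "Solicited local or systemic adverse event leading to the subject withdrawing from the study" (or being withdrawn from it by the investigator), and that criterion carries the endpoint's own label.

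For a subject who stops vaccination, Section 9.2 says "Primary reason relative to premature discontinuation of the study vaccine(s) will be documented on the Vaccine Administration page/screen of the eCRF". A solicited adverse event is one of the listed reasons. The same section allows the subject to continue with study procedures.

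**The concern.** A subject who gives up the remaining doses because of a reaction, yet stays for follow-up, provides direct evidence on tolerability. Tolerability of co-administration is a primary objective. Under 12.5.8.3.2 this subject has an AE leading to withdrawal; under 12.5.3.1 the same event does not meet the withdrawal criterion. If the narrower rule decides what reaches the analysis file, the reported percentage will be lower than the broader definition implies, and a reader of the study report could not tell which definition was used.

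**Working it through.** The plan gives no count or rate for this endpoint, so there is no figure to reproduce. The check is to follow one case through the rules.

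**Case.** A subject records a solicited reaction in the eDiary. It is not serious, is not medically attended and resolves within 30 days. The subject declines the next dose and stays in the study.

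1. *Can this happen?* Yes. Section 9.2 lets a subject withdrawn from vaccine continue. Doses are given on Days 1, 61 and 91, so the case can arise after the first or second vaccination. After the third, no dose is left to decline.
2. *Where is the reaction recorded?* Section 8.2.1 keeps solicited AEs of the 7-day period in the eDiary and out of the eCRF. Section 12.5.8 makes the diary the only permitted source document for them after the first 30 minutes.
3. *Must it move to the AE eCRF?* Section 12.5.3.1 has three triggers: medical attendance, study withdrawal and seriousness. None is met.
4. *Is there a withdrawal flag on the AE page?* The one described is in Section 9.1: "This AE must be identified on the AE eCRF page by indicating" withdrawal from the study. That scope is natural in a section on study discontinuation, but no AE-page counterpart for vaccine withdrawal is described.
5. *Where is the reason for stopping?* On the Vaccine Administration page (Section 9.2).
6. *What does the SAP analyse?* Section 5.5.1.3 covers AEs recorded in the AE eCRF. It does not define AEs leading to withdrawal and names no Vaccine Administration field.

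The event therefore belongs to the endpoint as 12.5.8.3.2 defines it, and no stated rule carries it there. The gap is specific to solicited AEs, because Table 3 and 12.5.4 already require unsolicited AEs leading to vaccine withdrawal to be recorded.

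**Size, for illustration only.** Assume that a fraction p of the 315 subjects in a group are such cases:

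- p = 0.5%: 0.005 × 315 = 1.6 subjects
- p = 2%: 0.02 × 315 = 6.3 subjects

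This is about 2 to 6 per group. The range for p is an assumption; neither document supports a particular value.

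**The case against.** The best reply is that 12.5.3.1 says when AE eCRF entry is mandatory and forbids nothing else, and that other routes exist:

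- Section 12.5.8.3.2 asks the investigator to evaluate AEs for study or vaccine withdrawal, and requires contact with the subject when symptoms were of concern.
- Severe solicited reactions trigger site alerts (12.5.8.1.1).
- Newly reported verbal information goes to the eCRF as an unsolicited AE (12.5.8), as does a solicited AE reported as unresolved after 30 days (12.5.8.2).
- Section 8.6.1 provides an interview when a subject is withdrawn from treatment.
- SAP 5.5.1.1 expects some solicited AEs to appear in both the eCRF and the eDiary.

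This stands to the extent that a reader might infer such subjects are never counted, which the documents do not support. It does not close the gap. A diarised reaction is not new information. The case traced resolves within 30 days. The 8.6.1 procedures end with the termination page, which does not fit someone who stays. The evaluation in 12.5.8.3.2 names no form for a diary-only event.

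It is also fair to say that the reaction itself is not hidden: it is reported by severity under a separate primary endpoint. What may be lost is its link to stopping vaccination.

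**Conclusion.** The definitions conflict, and for solicited reactions the stated recording and analysis rules can under-count the endpoint as 12.5.8.3.2 defines it. Such a subject may be missed; whether that happens in practice depends on eCRF guidance and site habits that the documents do not show. The 2 to 6 subjects per group rest wholly on the assumed 0.5% to 2%. Safety is descriptive, with no between-group tests, and the non-inferiority conclusions are untouched. This should be corrected, but it is a limited point.

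Four further readings are tempting but not supported:

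- **Bias between groups.** Only one group receives two active vaccines at Visit 1, so a reader might expect omissions to concentrate there. No document gives discontinuation by group, and Group MenB also receives rMenB+OMV NZ at that visit.
- **A COVID-19 restriction.** SAP 5.5.1.3 lists "Adverse event leading to withdrawal with relationship to COVID-19". SAP 5.1.2 uses similar wording for breakdowns, and 5.5.1.3 separately commits to percentages from Day 1 to Month 9 without any such limit. It reads as a breakdown.
- **Omission of the 30-day endpoint.** One bullet in SAP 5.5.1.3 mentions only unsolicited AEs, but SAP Section 2 restates the full 30-day endpoint and the AE summaries are to be given by interval.
- **Support from Section 7.7.** That section lists contraindications to further doses. It does not deal with a subject who declines a dose after pain or fever; Section 9.2 is the relevant text.

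**What to change.** 1. **Protocol.** Apply the 12.5.8.3.2 definition, study or vaccine withdrawal, in 12.5.3.1 (second criterion), 12.5.8.2 and the corresponding row of Tables 15 and 16.
2. **SAP 5.5.1.3.** Define the term in the same way. Derive the endpoint from both the AE-page flag and the adverse event reasons on the Vaccine Administration page (expedited, non-serious, unsolicited and solicited).
3. **Tables.** Report vaccine withdrawal, study withdrawal and either, by group, for each 30-day window and for Day 1 to Month 9. A reader can then recover whichever definition is wanted.

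The cost is a protocol clarification and some SAP wording. The discontinuation reason is already collected, so the analysis change needs no new data and alters no rule on who is vaccinated. The reported percentage may rise slightly. One limit remains: the Vaccine Administration page holds only the primary reason, so a subject coded simply as unwilling to be vaccinated would still not be identified.
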